**Research Title:**

**Effects of Osteopathic Manipulative Treatment (OMT) and Bio Electro-Magnetic Energy Regulation (BEMER) Therapy on neck pain in adults.**

**Research Purpose:**

The purpose of this project is to investigate the individual and combined effects of Osteopathic Manipulative Treatment (OMT) and Bio Electro-Magnetic Energy Regulation (BEMER) Therapy on neck pain in adults.

**Study Summary:**

Neck pain is a prevalent complaint made by patients to their physician [1, 2]. Many treatment approaches exist depending on the specific etiology, however, there still remains a need for more conclusive evidence regarding many treatment strategies [3-6].

Osteopathic Manipulative Treatment (OMT) is commonly utilized for an array of musculoskeletal and various other complications including neck pain. Goals of this treatment strategy include myofascial tissue release, decreased pain, and increased range of motion.

Bio Electro-Magnetic Energy Regulation (BEMER) therapy is a therapeutic modality that deploys a biorhythmically defined stimulus through a Pulsed Electromagnetic Field (PEMF), which leads to an increase in blood flow. The positive effects of BEMER on the circulation has been shown to result in significant increases in arteriovenous oxygen difference, number of open capillaries, arteriolar and venular flow volume, and flow rate of red blood cells in the microvasculature [7, 8]. BEMER with physiotherapy has shown reduction in pain and fatigue acutely in patients with chronic low back pain [9]. A systematic review of randomized controlled trials that investigated whether PEMF was effective in low back pain showed there was a decrease in pain intensity and improved functionality in individuals with different low back pain conditions [10].

By this mechanism, it is plausible that the combination of OMT and BEMER therapy may help increase circulation to myofascial structures that influence neck restriction and pain. The purpose

of this study is to investigate the individual and combined effects of OMT and BEMER therapy on neck pain.

### **Review of Literature:**

Neck pain is estimated to have a prevalence of 30% annually and perhaps, affect 70% of patients at some point in their life [1, 2]. Neck pain has become a very important public health problem, and social issue due to its high prevalence, unsatisfactory treatment options, large medical burden, and reduction in quality of life [11]. In fact, neck pain ranks fourth worldwide as a cause of Years Lived with Disability [12]. Many complaints of acute or chronic neck pain are musculoskeletal in nature and present with significant muscular tension in the neck, which may restrict blood flow.

Neck pain can result from a variety of etiologies, including postural, neurological and mechanical causes such as muscle strains, joint damage, and nerve compression [2]. Several treatment options are currently available for the various causes of neck pain such as nonsteroidal anti-inflammatory and steroid pharmacotherapy, surgery, and an array of more conservative treatments including Osteopathic Manipulative Treatment (OMT). Palpation of the posterior and anterior neck muscles for tissue texture changes and tender points can assist in the diagnosis of cervical dysfunctions [13]. The upper cervical and upper thoracic regions can contribute to temporomandibular joint (TMJ) dysfunction through the continuity of fascia. The utilization of OMT on these somatic dysfunctions can be greatly beneficial to these patients. Dysfunction of the occiput and atlas is associated with the temporal bone and these tender points located between the ramus of the mandible and mastoid process can be effectively treated with counterstrain, which is an osteopathic manipulative technique [13].

There have been conflicting reports that investigated the effects of spinal manipulation (an osteopathic manipulative technique) on neck pain [1, 14-22]. For example, patients with acute and subacute neck pain who received treatment with spinal manipulative therapy experienced significant pain relief compared with medication at 8, 12, 26, and 52 weeks, proving to be more effective for both short and long term pain relief [1]. On the other hand, Fredin & Loras suggested that combined treatment consisting of manipulation therapy and exercise therapy does not seem to be more effective in reducing neck pain intensity at rest, neck disability or improving quality of life in adult patients with grade I-II neck pain, than exercise therapy alone [18]. These discrepancies may be explained by differences in the specific therapeutic techniques, duration of the intervention, and characteristics of the sample population. It is clear that additional research investigating the effects of alternative treatments on neck pain is warranted.

Specific OMT approaches have been studied for the treatment of patients presenting with neck pain, but substantially less than other general complaints such as lower back pain [3, 23, 24]. In one study, it was demonstrated that treating somatic dysfunction of the cervical spine with OMT in patients with acute neck pain provides pain relief and significantly reduces pain intensity when compared to intramuscular administration of ketorolac tromethamine [21]. The authors concluded that OMT is a reasonable alternative to parenteral nonsteroidal anti-inflammatory medication for patients with acute neck pain [21]. In addition, a specific osteopathic manipulative treatment called muscle energy has been shown to provide significant relief of neck pain and improve cervical range of motion [20]. Although there is some evidence to suggest OMT may be an alternative to the treatment of neck pain [20, 21], there is a clear need to better understand the effects of OMT specifically on subacute and chronic neck pain.

Bio-Electro-Magnetic-Energy-Regulation (BEMER) therapy is a therapeutic modality that deploys a biorhythmically defined stimulus through a Pulsed Electromagnetic Field (PEMF), which leads to an increase in blood flow. The positive effects of BEMER on the circulation has been shown to result in significant increases in arteriovenous oxygen difference, number of open capillaries, arteriolar and venular flow volume, and flow rate of red blood cells in the microvasculature [7, 8]. Although there has not been any studies on the effects of BEMER on neck pain, BEMER with physiotherapy has shown reduction in pain and fatigue acutely in patients with chronic low back pain [9]. A systematic review of randomized controlled trials that investigated whether PEMF was effective in low back pain showed there was a decrease in pain intensity and improved functionality in individuals with different low back pain conditions [10]. By this mechanism, it is plausible that the combination of OMT and BEMER therapy may help increase circulation to myofascial structures that influence neck restriction and pain. With promising evidence, there remains ample opportunity to study treatment modalities and the use of complementary techniques and therapies combined with OMT [4, 6, 16]. The purpose of this study is to investigate the individual and combined effects of OMT and BEMER therapy on neck pain.

In summary, there is generally moderate and favorable evidence supporting the utility of OMT, and a growing body of evidence regarding BEMER therapy. However, plentiful literature also indicates the need for further exploration of these therapies individually as well as in combination, and their effect on neck pain. It is a goal of this project to further investigate the effects of individual and combined therapies in a controlled, single-blinded study.

## **Methodology**

### **I. Study Design**

A. Prospective, noninvasive study to examine the individual and combined effects of OMT and Bio Electro-Magnetic Energy Regulation (BEMER) therapy on neck pain in adults.

#### **B. Study treatment location**

1. All treatments and post treatment measurements will be performed in the osteopathic manipulative therapy laboratory at Lake Erie College of Osteopathic Medicine, Bradenton. [name], a licensed osteopathic physician, will be on call in the vicinity of the treatment location, however not necessarily in the room of treatment. [name] will be in the building and, if not in the treatment room, will be available by phone and/or text message at all times during treatments and will respond immediately to matters involving the study participants and/or treatments. She will have access to participant schedules and times, so that her schedule can accommodate any and/or all circumstances requiring her immediate assistance. All researchers will have her contact information available and readily accessible as a requirement of participation.

#### **C. Data Collection**

1. After written consent is obtained, the study coordinator will assign the participant a randomized study number to de-identify the participant.

2. To achieve our project's goal, we will have 4 separate groups (OMT, BEMER, OMT+BEMER, and Combined Placebo of OMT+ Sham BEMER). All treatments will be performed by osteopathic medical students. [name] will provide students

- additional training on OMT and placebo treatments, and [name], a BEMER representative, will provide additional training on BEMER treatments.
3. To control for anchoring bias, subjects will be randomized into one of the four groups: OMT, BEMER, OMT+BEMER, and Placebo.
- D. Osteopathic Manipulation Diagnosis and Treatment Protocol (OMT)
1. Osteopathic Diagnosis and Screening
    - a) Screening Special tests: Spurling's test, Wallenberg test
    - b) Observe and Palpate Cervical and Thoracic spine muscles for TART (tissue texture change, asymmetry, restriction of motion, and tenderness) changes- AROM and PROM of the cervical spine (using head and neck motion for T1-4)
    - c) OA (atlanto-occipital joint), AA (atlanto-axial joint), C2-C7 (cervical vertebrae 2-7), and T1-4 (thoracic vertebrae 1-4) intersegmental diagnosis
    - d) TMJ (temporomandibular joint) assessment – opening and closing of jaw
    - e) Counterstrain Tenderpoint screening for the following muscles: Medial pterygoid, Anterior C7, Anterior C8, Posterior C1 inion
    - f) 1st rib somatic dysfunction
  2. Osteopathic Manipulative Treatment/Techniques
    - a) Suboccipital Release (constant inhibitory pressure), supine – myofascial release/soft tissue technique
    - b) Contralateral Traction, supine - soft tissue technique
    - c) Upper thoracic spine unilateral prone pressure, prone - soft tissue technique
    - d) Direct or Indirect Thoracic inlet/outlet, supine – myofascial release technique
    - e) Occipitoatlantal somatic dysfunction muscle energy (post-isometric relaxation) supine
    - f) Atlantoaxial somatic dysfunction muscle energy technique (post-isometric relaxation) supine
    - g) C2-C7 somatic dysfunction muscle energy technique (post-isometric relaxation) supine
    - h) T1-4 Dysfunction muscle energy technique (post-isometric relaxation) - seated
    - i) 1st rib elevation dysfunction – articular technique – seated
    - j) Direct or indirect Sub mandibular release, supine - myofascial release technique
    - k) Counterstrain technique for the following muscles/locations: Medial pterygoid, Anterior C7, Anterior C8, Posterior C1 inion
  3. Second year osteopathic medical students will perform the duties of diagnosing and screening for somatic dysfunction in these regions (as listed above). These same 4-6 students will also be trained to perform all of the treatment modalities by the osteopathic principles and practice (OPP) course director and OPP clinical faculty at LECOM-Bradenton.
  4. Explanation of each Osteopathic Manipulative Treatment (OMT) technique and screening tests
    - a) Myofascial release (MFR) is a system of diagnosis and treatment which engages continual palpatory feedback to achieve release of myofascial tissues [25]. MFR can be performed in a direct or indirect manner. If direct MFR is being performed the area of myofascial tissue restriction is engaged for the myofascial tissues and the tissue is loaded with a constant force until tissue release occurs. If indirect MFR

is being performed the area of the body with dysfunctional myofascial tissues are guided along the path of least obstruction until free movement is achieved. For this study, the student doctors will perform MFR in the suboccipital and cervical regions with the patient lying on their back.

b) Soft tissue (ST) is a system of diagnosis and treatment directed toward tissues other than bony or joint origins [25]. Soft tissue technique involves direct engagement of myofascial tissues and is applied with lateral stretching, linear stretching, deep pressure, traction and/or separation of muscle origin and insertion while monitoring tissue response and motion changes by palpation. Soft tissue techniques will be applied to the cervical and thoracic regions in this study.

c) Muscle energy (ME) is a form of osteopathic manipulative diagnosis and treatment in which the patient's muscles are actively used on request, from a precisely controlled position, in a specific direction, and against a distinctly executed physician counterforce [25]. We will use muscle energy technique in the cervical spine and thoracic regions in the supine position in this study.

d) Counterstrain (CS) technique is a system of diagnosis and treatment that considers the dysfunction to be a continuing, inappropriate muscle/tendon/ligament strain reflex, which is stopped by applying a position of mild strain in the direction exactly opposite to that of the reflex; this is accomplished by specific directed positioning about the point of tenderness to achieve the desired therapeutic response [25]. We will screen for counterstrain tender points associated with medial pterygoid, sternocleidomastoid, Suboccipital muscles. These muscles have attachments to the temporal bone, mandible, occiput, cervical spine, and clavicle and have been postulated to be a contributing factor to musculoskeletal causes of neck pain [26].

e) Articular treatment (ART) is a low-velocity-to high-amplitude technique where a joint is carried through its full motion with the therapeutic goal of increased freedom with range of movement. The activating force is either a springing motion or repetitive concentric movement of the joint through the restrictive barrier. The technique may be direct, indirect, or combined, and there can be a variation of rhythms, amplitude, or acceleration catered to the patient's presentation. This technique is indicated when there is presence of articular or myofascial somatic dysfunction, as well as circulatory and lymphatic congestion [25]. In this study student doctors will use an articular technique to treat a 1st rib elevation dysfunction.

f) Spurling's Test/Maneuver - This test will assess for cervical nerve root irritation or compression. The test is performed with the subject in the seated position. The evaluating student will then place the subjects head and neck in an extended and sidebent position towards one side. Once in this position, a gentle but deliberate compressive force will be applied from the top of the subjects head. If this maneuver produces a radicular pain in a distinct dermatomal pattern down the affected sides upper extremity then the test is considered positive. A positive test will exclude the subject from the study. The test is performed bilaterally [10].

g) Wallenberg test - This test will assess for possible vertebral artery insufficiency. The test is performed with the subject in the supine position. The evaluating student will then place the subjects head and neck in an extended

position and then rotate the head and neck to one side. This position will be held for 30 seconds. If at any time the subject complains of dizziness, visual changes, lightheadedness and/or the evaluating student notes eye nystagmus then this is considered a positive test. A positive test will exclude the subject from the study. The test is performed bilaterally [27].

E. Bio Electro-Magnetic Energy Regulation (BEMER)

1. Protocol

a) Subject will lay supine on the BEMER mat, and place the B.Pad® on their cervical neck. BEMER mat intensity 3 will be selected in week 1, intensity 4 for week 2, and intensity 5 for week 3. B.Pad® will be set at Program 1 for the duration of the intervention. Treatments last approximately 15-25 minutes.

2. Explanation of BEMER

a) BEMER is a therapeutic modality that deploys a biorhythmically defined stimulus through Pulsed Electromagnetic Field (PEMF). This stimulus has a targeted effect on the microvasculature, and the primary effect is an improvement in tissue microcirculation [9]. The positive effects of vasomotion (i.e. opening of the blood vessels) on the microcirculation has been shown to result in significant increases in arteriovenous oxygen difference, number of open capillaries, arteriolar and venular flow volume, and flow rate of red blood cells in the microvasculature [7, 8]. Therefore, BEMER can potentially be used in the treatment of neck pain by improving microcirculation in muscular tissue. Last year we have successfully utilized the BEMER therapy without any adverse effects in a prior study on low back pain.

F. Placebo

1. Placebo (Combined light touch and BEMER Sham): Treaters will place their hands lightly on the subject's cervical paraspinal muscles in the supine position in the same area as one would place their hands for cervical MFR, and on the subjects upper thoracic paraspinal muscles in the prone position in the same area as one would place their hands for thoracic MFR (approximately 5 minutes). However, no pressure or action will be done. In addition, the subject will lie down on the BEMER mat (as they would do during a BEMER session), but the device will not be activated. This treatment will be used as a control.

G. The research assistants will individually coordinate experimental times with the subjects. A licensed osteopathic physician will be in the vicinity of the treatment location at all times while treatments are being given.

H. OMT, BEMER, and placebo will be performed by osteopathic medical students who have completed additional training given by a licensed osteopathic physician to ensure uniform technique. A licensed osteopathic physician will be in the vicinity of the treatment location at all times while treatments are being given.

I. All data collection logs will be de-identified of personal information and only contain the randomized participant ID number linking the participant to the data collected.

J. The identifying information will be maintained by the principal investigator in a locked cabinet, which they alone have access to.

II. Study Procedures and Timeline

A. Study duration

1. The study duration is three weeks. The subjects will be required to have either OMT, BEMER, OMT+BEMER, or Placebo treatments during the course of the study. Each subject in the OMT groups (i.e. OMT and OMT+BEMER) will receive treatment 3 times per week for a period of 3 weeks. Subjects in the BEMER groups (i.e. BEMER and OMT+BEMER) will receive treatment 5 times per week for a period of 3 weeks. Finally, subjects in the Placebo group will receive the combined light touch and BEMER sham treatments at same intervals as the corresponding experimental groups. OMT, BEMER, and placebo treatments will be performed by osteopathic medical students who have completed additional training given by a licensed osteopathic physician, to ensure uniform technique.
2. Recruitment:
  - a) LECOM-Bradenton faculty, staff, osteopathic medical, dental, pharmacy, and master's students will be informed via email of the opportunity to participate in the research study and will be given contact information to confirm eligibility with a study coordinator (Appendix A).
3. Experimental Sessions
  - a) Following written consent (Appendix B), subjects will be given a randomized study ID number. They will be randomized into their treatment group.
  - b) Each subject in the OMT groups (i.e. OMT and OMT+BEMER) will receive treatment 3 times per week for a period of 3 weeks. As previously mentioned, subjects in the BEMER groups (i.e. BEMER and OMT+BEMER) will receive treatment 5 times per week for a period of 3 weeks. Finally, subjects in the Placebo group will receive the combined light touch and BEMER sham treatments at same intervals as the corresponding experimental groups. OMT, BEMER, and placebo treatments will be performed by osteopathic medical students who have completed additional training given by a licensed osteopathic physician, to ensure uniform technique. All treatments will be performed during the span of three consecutive weeks.
  - c) Subjects will complete brief questionnaires regarding neck pain and quality of life before the beginning of study and will complete the same questionnaires following the completion of the three week treatment (Appendices C, E, F).

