### III. Analysis

#### A. Study Statistics

1. Primary outcome variable
  - a) Questionnaire ratings before and after treatments
    - (1) Neck Disability Index (Appendix E) [28-31]
    - (2) SF-12 Health Survey (Appendix F) [32]
    - (3) Visual Pain Analog (Appendix C) [33]
2. Statistical plan including sample size justification and interim data analysis
  - a) Paired T-tests (N~10 subjects) to investigate the changes in neck pain after each treatment protocol.
  - b) One-Way ANOVA to investigate any statistically significant differences between the means of each of the 4 experimental groups.
3. Early stopping rules

- a) Any adverse effect, as determined by the attending licensed osteopathic physician. No adverse effects are anticipated.
- B. Blinding
  - 1. All outcome analyses will be performed in a blinded fashion. Subject survey and corresponding data will be de-identified and analyzed retrospectively by investigators with no exposure to the treatment sessions. Doing so will eliminate bias associated with investigator self-interest and ensure subject anonymity.

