## **Appendices**

### **Appendix A: Recruitment email**

The LECOM Student American Academy of Osteopathy (SAAO), is conducting a study, and we would like to welcome all LECOM faculty, staff, and students to participate. The study will evaluate the individual and combined impact of osteopathic manipulative treatment (OMT) and Bio Electro-Magnetic Energy Regulation (BEMER) therapy on neck pain.

This study will take place over a three-week period. Each subject in the OMT group will receive treatment 3 times per week for a period of 3 weeks. Subjects in the BEMER groups will receive treatment 5 times per week for a period of 3 weeks. Each subject in the OMT+BEMER group will receive OMT 3 times per week and BEMER therapy 5 times per week for a period of 3 weeks. Subjects will complete brief questionnaires regarding neck pain and quality of life before the beginning of study and will complete the same questionnaires following the completion of the three week treatment. Each treatment will be individually scheduled with your assigned study coordinators. Each treatment session will last approximately 10-30 minutes.

You will be compensated with a \$50 gift card for your time.

If you are interested and would like to learn more about the study, please contact [name] at [[contact]](mailto:[contact]) for more information.

Thank you for your consideration in helping with this very important research.

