### **Appendix C: Visual Analog Scale**

The Visual Analog Scale (VAS) is a 100-millimeter line with “no pain” on one end and “pain as bad as it can be” at the other end. This scale is a very simple form of assessment. Patients are expected to mark on the line the amount of pain they are experiencing.

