#### Section 1: Pain Intensity

- = I have no pain at the moment
- = The pain is very mild at the moment
- = The pain is moderate at the moment
- = The pain is fairly severe at the moment
- = The pain is very severe at the moment
- = The pain is the worst imaginable at the moment

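### The pain outcome rests on one momentary VAS mark at each end and an unadjusted comparison; a second untreated baseline mark, baseline adjustment and a few marks just after treatment would recover precision cheaply

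*Combined protocol and SAP*

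**What the plan says.** Methodology II.A.3.c has subjects complete the questionnaires "before the beginning of study and will complete the same questionnaires following the completion of the three week treatment". The recruitment email (Appendix A) describes the same two occasions. Appendix C defines the VAS as a 100 mm line with no recall period: "Patients are expected to mark on the line the amount of pain they are experiencing". The first NDI item is also about the present; its lowest option is "I have no pain at the moment".

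Methodology III.A.1 lists NDI, SF-12 and VAS together as primary. III.A.2 gives the only sample-size figure, "Paired T-tests (N~10 subjects", for the within-arm tests. It adds a one-way ANOVA across the four arms, names no covariate, and does not say whether post-treatment scores or changes are compared. The cost section budgets for 40 subjects.

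Subjects attend often. In II.A.3.b, "Each subject in the OMT groups (i.e. OMT and OMT+BEMER) will receive treatment 3 times per week for a period of 3 weeks", while the BEMER groups "will receive treatment 5 times per week for a period of 3 weeks". Appendix A says the combined arm "will receive OMT 3 times per week and BEMER therapy 5 times per week for a period of 3 weeks". For the control, "subjects in the Placebo group will receive the combined light touch and BEMER sham treatments at same intervals as the corresponding experimental groups".

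**The concern.** A single mark of current pain mixes the subject's usual level with whatever that day brought. The plan takes one such mark at each end, and its between-arm test does not use the baseline mark as a covariate. Both choices leave avoidable variance in a primary outcome.

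At about 10 per arm this matters. Assuming two-sided 5% and 80% power (the plan states neither), a pairwise comparison can detect only about 1.32 SD of the analysed score. Recruitment is confined to one campus, so measuring pain more precisely is one of the few inexpensive ways to improve that.

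**Working it through.** **Inputs from the documents.** One VAS before and one after; about 10 per arm, 4 × 10 = 40 in total. Visits: OMT 3 × 3 = 9; BEMER 5 × 3 = 15; combined arm 15 if OMT falls on BEMER days, 9 + 15 = 24 if booked separately (not stated); placebo 9 to 15. The documents give no SD, reliability, correlation, alpha, power or target effect, so the figure of 10 per arm cannot be reproduced.

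**Assumed inputs.** Single-rating variance is set to 1. *rb*, the correlation of a baseline mark with a post-treatment mark, is 0.3-0.6. *r1*, the correlation of two marks a few days apart, is 0.7-0.9. Nearby marks should agree better than marks three weeks apart, hence *r1* > *rb* ("decaying" below, without implying any wording of the plan).

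**1. Baseline adjustment.** ANCOVA residual variance is 1 − rb². Against an unadjusted post-score comparison the cut is rb²: 0.3² = 9%, 0.6² = 36%. If the ANOVA was meant for changes, with variance 2(1 − rb), the cut is (1 − rb)/2: 35% at 0.3 and 20% at 0.6.

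**2. Second untreated baseline mark.** Residual variance becomes 1 − 2rb²/(1 + r1).
- rb 0.3, r1 0.9: 0.910 → 0.905, a cut of 0.5%.
- rb 0.6, r1 0.7: 0.640 → 0.576, a cut of 9.9%.
- All correlations equal to ρ, 1 − 2ρ²/(1 + ρ): at 0.4, 0.840 → 0.771 (8%); at 0.9, 0.190 → 0.147 (22%).

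**3. Mean of three post-treatment marks, one baseline.** Variance of the mean: V3 = [3 + 4r1 + 2·max(r1², rb)]/9. Residual: V3 − rb².

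| r1 | rb | One mark | Mean of three | Cut |
|---|---|---|---|---|
| 0.9 | 0.3 | 0.910 | 0.913 − 0.090 = 0.823 | 9.5% |
| 0.9 | 0.6 | 0.640 | 0.913 − 0.360 = 0.553 | 13.5% |
| 0.7 | 0.3 | 0.910 | 0.753 − 0.090 = 0.663 | 27% |
| 0.7 | 0.6 | 0.640 | 0.778 − 0.360 = 0.418 | 35% |

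A cut of 10-35% shrinks the detectable difference by 5-19% (1 − √0.90; 1 − √0.65). It is worth having 10/0.90 ≈ 11 to 10/0.65 ≈ 15 subjects per arm instead of 10.

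**4. Steps 2 and 3 together**, against ANCOVA with one mark at each end: at the weak corner 0.913 − 0.095 = 0.819 against 0.910 (10%); at the strong corner 0.778 − 0.424 = 0.354 against 0.640 (45%).

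**5. Why the extra marks should follow the last session.** Suppose improvement is linear in sessions and pain is marked before treatment on Monday, Wednesday and Friday of week 3. The OMT arm has then had 6, 7 and 8 of 9 sessions (mean 7/9 = 78%). The BEMER arm has had 10, 12 and 14 of 15 (mean 12/15 = 80%). So 20-22% of the effect is missing. To break even, variance must fall by 1 − 0.80² = 36% to 1 − 0.778² = 40%, which is above the whole 10-35% range in step 3.

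These formulas ignore the degree of freedom spent on the covariate and chance baseline imbalance. Both trim the smallest gains slightly at this sample size.

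**The case against.** The strongest reply is that one VAS before and one after is a legitimate design. Nothing in the plan contradicts it, and the documents contain no figure showing that daily variation is a large part of the error. That stands: the direction of the gain is certain for any within-person correlation below 1, but its size is not.

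A reader might infer more, namely that subjects are in the laboratory anyway, so averaging marks taken before the week 3 sessions would raise power at almost no cost. With every correlation set to 0.6, three post marks lower residual variance from 0.640 to 0.373, and the pairwise detectable difference (1.33 × √variance, 17 df) from 1.06 to 0.81 SD. The documents do not support that reading:
- It assumes marks days apart agree no better than marks three weeks apart with treatment between them.
- It ignores dilution. Dividing 0.8126 by 0.80 and by 0.7778 gives 1.02 to 1.04 SD on the full-effect scale, hardly better than 1.06.
- II.A.3.c places the outcome after completion of treatment; marks before week 3 sessions answer a different question.

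If improvement has largely levelled off before week 3, those marks would still help. The documents do not say, and the BEMER mat setting rises to its highest in week 3, so a plateau cannot be presumed.

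Two further objections stand in part. Sessions are scheduled individually, so matched days must be counted from the last session rather than set by weekday. And ANCOVA is not the planned analysis; however, averaging three post marks also lowers change-score variance, by 11-30% for reliability 0.5-0.8 and 6-18% at 0.9, assuming independent daily errors and a pre-post correlation of true levels of 0.5-0.9. Serially correlated errors reduce this: at an autocorrelation of 0.5, three marks remove 39% of the transient variance rather than 67%.

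**Conclusion.** The point holds as an inexpensive gain in precision on one primary outcome, and is worth considering rather than required. Baseline adjustment is worth 9-36% of the variance of an unadjusted post-score comparison. A second baseline mark adds about 1-10% under decaying correlation, or 8-22% if all correlations are equal at 0.4-0.9. Three post-treatment marks cut residual variance by about 10-35% under decaying correlation. Every correlation is an assumption.

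The second-baseline figure also needs consent and session 1 to fall on different days, which the plan does not state; two marks on the same day would add little. The post-treatment figure assumes that benefit does not fade appreciably over the few days averaged.

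It would be wrong to conclude that the single marks invalidate the pain outcome, or that repeated marks cure the small sample. The NDI and SF-12 are unaffected (most SF-12 items ask about four weeks), and the missing sample-size justification remains.

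**What to change.** - **II.A.3.c and Appendix C, baseline:** take the VAS at consent and again immediately before session 1, and average the two. Do not use later week 1 marks as baseline; they follow treatment, and by different amounts across arms.
- **II.A.3.c and Appendix C, outcome:** repeat the VAS as a paper mark on two or three set days just after the last session, the same days in all arms, and name their average as the pain outcome. State what is done when a mark is missing.
- **III.A.2.b:** compare arms on post-treatment VAS by ANCOVA adjusted for mean baseline VAS.
- **Week 3 marks before sessions,** if collected: secondary only.

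The cost is a few extra marks per subject and their data entry. The post-treatment marks may fall after the last scheduled visit and so need collecting. The outcome becomes average pain over the days just after treatment rather than pain at a single moment.
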